The sample size was estimated for the primary outcome utilizing a two-sided likelihood ratio chi-square test of two independent proportions. The following parameters were used in this calculation: alpha of 0.05 and a power of 0.80. A response rate in the control group of fluticasone alone (reference proportion) was estimated to be 50% based on the study Konikoff et al.⁶ The estimated response rate for the treatment arms are based on clinical experience as was estimated to be in the range of 70% to 80%. This graph demonstrates that the sample size estimation may vary anywhere from 78 to 180 subjects. We plan to enroll approximately 100 patients.

11.3 Total number of subjects requested (including records and specimens):

100

11.4 If you are recruiting by study arm, please identify the arms of the study and how many subjects will be enrolled in each arm

50 subjects in each arm - one arm will be fluticasone and placebo, one arm will be fluticasone and omeprazole.

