13.3 Please describe the pre-screening process. If no pre-screening, enter Not Applicable in the text editor

Subjects will be identified through the primary Gastroenterologist in adult and pediatric gastroenterology clinics at Walter Reed National Military Medical Center. No HIPAA preparatory research provision will be required. Once a patient has been consented, the investigator will determine if the study subjects meets eligibility criteria.

13.4 Consent Process:

Are you requesting a waiver or alteration of informed consent?

Yes No

Please explain the consent process:

Once a subject has been referred, they will then meet with one of the GI nurses to schedule their EGD. At that time, an investigator will explain the study at length, answer any questions, and administer the informed consent. Subjects will be reminded that enrollment is purely voluntary and that they will receive the standard of care, regardless of whether they choose to enroll or not. The parent or guardian of children 6-17 years old will be asked to sign a consent form prior to study enrollment, and all questions will be answered. Any subjects between the ages of 8-17 years will also be provided an Assent

form to help provide additional age appropriate information regarding the study. If a subject turns 18 years old during the study time frame, he or she will need to be consented when they return for their next office visit.

13.5 DoDI 3216.02 requires an ombudsman to be present during recruitment briefings when research involves greater than minimal risk and recruitment of Service members occurs in a group setting. If applicable, you may nominate an individual to serve as the ombudsman.

- N/A
- Propose ombudsman

13.6 Withdrawal from Study Participation:

Explain the process for withdrawal and specify whether or not the subjects will be given the opportunity to withdraw their data their data/specimens in the event they wish to withdraw from the study

In the consent form, the patient's right to withdraw from study participation is covered in detail. Subjects must notify the primary investigator via phone or email and return all study medication if they decide to withdraw. By leaving the study at any time, subjects will not risk losing their right to medical care or benefits within the military treatment facility. Subjects who withdraw will be referred to their primary gastroentetologist for continued care in accordance with acceptable standards of medical treatment.

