14.0 Risks and Benefits

14.1 Risks of Harm:

Identify all research-related risks of harm to which the subject will be exposed for each research procedure or intervention as a result of participation in this study. Consider the risks of breach of confidentiality, psychological, legal, social, and economic risks as well as physical risks. Do not describe risks from standard care procedures; only describe risks from procedures done for research purposes

Research participants will not be exposed to any more risks than what are experienced by non-study patients being evaluated and treated for Eosinophilic Esophagitis. All interventions are within standard of care parameters in either treatment or control arm. It should be noted that there are risks associated with the EGD procedure to include bleeding, pain, infection, and intestinal perforation. There are also risks associated with the anesthetics used. However, patients who do not participate in the study would be subject to the same frequency and risks of EGD procedures.

14.2 Measures to Minimize Risks of Harm (Precautions, safeguards):

For each research procedure or intervention, describe all measures to minimize and/or eliminate risk of harms to subjects and study personnel

Safety Monitoring Plan

Participants will have cardiorespiratory monitoring throughout the endoscopic procedures, and will undergo pre procedure and post procedure monitoring per hospital protocol. The participant will receive a standard follow up call for biopsy results from the respective clinic, as is the standard of care for all patients who receive endoscopy. In addition, study participants will receive a telephone follow up 4 weeks after starting therapy.

Safety Analysis Plan

At the 4 week phone follow up, participants will be asked about any symptoms that have started since study treatment began. If worsening symptoms, patient will be brought in for a clinic visit to further evaluate ability to continue in trial.

14.3

Confidentiality Protections (for research records, data and/or specimens):

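### The 100 subjects in 11.2 to 11.5 serve as both total requested and 50 + 50 enrolled, with no loss allowance; 10.1 and Section 13 disagree on whom they count

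*Combined protocol and SAP*

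**What the plan says.** **Sample size.** Section 11.2, repeated in 11.5, sizes the trial for the binary primary outcome, "utilizing a two-sided likelihood ratio chi-square test of two independent proportions", with "alpha of 0.05 and a power of 0.80". The control response is 50%, and the combination arm is put at 70% to 80% from clinical experience. The result is a range: "This graph demonstrates that the sample size estimation may vary anywhere from 78 to 180 subjects". The plan then settles on about 100. Section 11.3 requests 100 in total. Section 11.4, which asks how many will be enrolled in each arm, answers "50 subjects in each arm - one arm will be fluticasone and placebo" and gives the same number to fluticasone plus omeprazole.

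**Outcome and losses.** The primary outcome in 11.6 is fewer than 15 eosinophils per high power field, which after treatment can only come from the week-8 EGD. Section 13.6 describes how a subject withdraws. Section 14.2 provides that if symptoms have worsened by the week-4 call, the "patient will be brought in for a clinic visit to further evaluate ability to continue in trial". Neither gives an expected rate. The form at 11.1 asks how missing data will be handled. The answer refers to 11.4, which holds only the arm sizes, and 11.6 has no missing-data rule.

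**Who counts as enrolled.** Section 13.1 enrols a referred subject once consent is given. Section 13.3 adds: "Once a patient has been consented, the investigator will determine if the study subjects meets eligibility criteria". Section 13.4 places consent at the meeting where the EGD is scheduled. Section 10.1, by contrast, defers enrolment and randomisation until the PPI course is complete and the initial EGD has given a diagnosis of EoE. Its schedule puts consent, randomisation and start of treatment on one day, with the initial endoscopy already available for review.

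**The concern.** A two-proportion calculation counts subjects who contribute an outcome. Here its result is carried unchanged into two other counts: the total submitted for approval and the number enrolled by arm. Requested and allocated numbers are equal, so there is no margin.

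Two things could reduce the number analysed. If the 100 is a ceiling on consents, patients consented and then found ineligible use it up before randomisation. Subjects without a week-8 biopsy reduce it after randomisation. The plan addresses neither, and its sections disagree on whether the first can happen. At stake are whether recruitment stops before 50 per arm are randomised, and whether a reader of 11.2 and 11.5 takes 0.80 to be the power that 100 enrolled will provide.

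**Working it through.** **Inputs (11.2, 11.4, 10.1).** Two-sided likelihood ratio chi-square test, alpha 0.05, target power 0.80, control response p1 = 0.50, treatment response p2 = 0.70 to 0.80, 1:1 allocation, 50 per arm. Loss rates are not given, so 90 and 80 analysed are assumptions.

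**Formula.** With n analysed per arm and pbar = (p1 + p2)/2, the noncentrality is

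lambda = 2n[f(p1) + f(p2)], where f(p) = p ln(p/pbar) + (1 − p) ln((1 − p)/(1 − pbar)).

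Power is the probability that a noncentral chi-square with 1 df exceeds 3.841. Power of 0.80 needs lambda = 7.849.

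**Reproducing the plan's range.**
- 50% vs 80%: pbar = 0.65 and f(p1) + f(p2) = 0.0472 + 0.0542 = 0.1013. Total N = 7.849/0.1013 = 77.4, or 39 per arm. That is the plan's 78 exactly.
- 50% vs 70%: pbar = 0.60 and the sum is 0.0204 + 0.0216 = 0.0420. Total N = 186.8, or 94 per arm, 188 in total. Pooled and unpooled normal formulas give 186 and 182. The stated 180 is slightly below all three and may have been read from the graph, which is not shown.

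Neither end contains a loss factor. Inflating 78 for a 10% loss, for example, would give 78/0.9 = 86.7, that is 87. So 78 to 180 counts evaluable subjects.

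**Power at the planned number and below.** For p2 = 0.75 the sum f(p1) + f(p2) is 0.0323 + 0.0354 = 0.0676. Lambda is 2n times each sum; at n = 50 it is 4.20, 6.76 and 10.13 for 70%, 75% and 80%.

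| Analysed (total) | 70% | 75% | 80% | Response needed for 0.80 |
|---|---|---|---|---|
| 100 | 54% | 74% | 89% | 76.8% |
| 90 (assumed) | 49% | 69% | 86% | 78.1% |
| 80 (assumed) | 45% | 64% | 81% | 79.6% |

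At 80% response, 39 per arm still gives 80.3% and 38 per arm gives 79.3%. The target therefore holds until fewer than 78 are analysed, a loss of up to 100 − 78 = 22.

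The table assumes that subjects without a biopsy are left out. If they were instead kept as non-responders, a 10% loss in both arms would turn 50% vs 80% into 45% vs 72% with 50 per arm, and power would be about 79%. The plan does not say which convention applies.

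**What the 100 counts.** If s of 100 consented patients prove ineligible, Section 13 leaves (100 − s)/2 per arm to randomise, which is below 50 for any s above zero. Under 10.1, s does not enter and 50 per arm can be randomised.

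**The case against.** A reader might infer that 50 per arm are to be analysed with a stated power of 0.80, and that this cannot be delivered. The documents do not support that. Section 11.4 is about subjects enrolled. No power is stated for 50 per arm; 0.80 is the input that produced 78 to 180, and about 100 was then chosen within that range.

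Screen failures are not certain to use up the total either. A patient found ineligible before randomisation belongs to no arm, so 11.4 reads naturally as randomised subjects, and 10.1 says outright that enrolment waits for the diagnosis. Section 13.4 does not say which EGD is being scheduled, although 13.1, which identifies patients by their presentation and need for endoscopy, points to the diagnostic one. A scenario in which half of those consented prove ineligible has no basis in the documents.

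Attrition may also be modest. Section 13.6 sets out a right to withdraw and is not a forecast. The week-8 EGD is described as standard of care, so stopping study drug need not mean no biopsy. At 80% response, 100 leaves 22 subjects to spare. At 70% and 75%, power is below 0.80 with nobody lost, so attrition deepens that shortfall without causing it.

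All of this stands. It does not remove the contradiction between 10.1 and Section 13 over enrolment, and it does not supply a loss allowance or a power figure for the number the trial will actually analyse.

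**Conclusion.** The point holds in a limited form. The plan computes evaluable subjects, uses 100 as both the total requested and the two arms combined, makes no allowance for losses, and gives conflicting accounts of who is enrolled. Followed literally, Section 13 prevents 50 per arm from being randomised as soon as one consented patient is ineligible; under 10.1 that problem does not arise.

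The 0.80 design power is not what 100 enrolled provides over most of the stated 70% to 80% range. Even with all 100 analysed it is reached only from about 76.8% upward, and with an assumed 90 or 80 analysed only from 78.1% or 79.6%. A 10% loss costs about 3 to 5 percentage points, so the larger part of the shortfall at 70% and 75% comes from choosing 100 within 78 to 180.

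These figures rest on the plan's 50% control rate, equal losses in both arms, and analysis of subjects with a biopsy only.

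**What to change.** 1. Reconcile 10.1 and its schedule with 13.1, 13.3 and 13.4, so that one point in the sequence of consent, diagnostic EGD and eligibility check counts as enrolment.
2. In 11.4, define 50 per arm as randomised subjects and state that patients consented but found ineligible do not count toward it.
3. In 11.3, give the number to be consented as a separate, higher ceiling, with the screen-failure rate assumed.
4. In 11.2 and 11.5, state the expected number with a week-8 biopsy (for example 80 to 90) and report the power across 70% to 80% response, or the response rate detectable with 0.80 power, for that number. Say how a missing biopsy is counted in that figure.

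The cost is a change of wording, a higher consent ceiling for the IRB to approve, and a less favourable stated power. These edits do not raise the power; they make the stated figure match the trial as planned, and they add no randomised patients. If the sponsor wanted 50 evaluable per arm instead, 100/(1 − d) would require 112 randomised at an assumed 10% loss or 125 at 20%; that is a separate decision.

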11.5 Please provide a justification for your sample size

The sample size was estimated for the primary outcome utilizing a two-sided likelihood ratio chi-square test of two independent proportions. The following parameters were used in this calculation: alpha of 0.05 and a power of 0.8. A response rate in the control group of fluticasone alone (reference proportion) was estimated to be 50% based on the study Konikoff et al (6). The estimated response rate for the treatment arms are based on clinical experience as was estimated to be in the range of 70% to 80%. This graph demonstrates that the sample size estimation may vary anywhere from 78 to 180 subjects. We plan to enroll approximately 100 patients.

11.6 Data Analysis Plan:

Outcome variables are listed in the following table. All continuous data will be evaluated for normality of the data using both univariate methods, visual inspection, and the Kolmogorov Smirnov test. Differences in continuous data that is normally distributed will be tested using parametric tests and for data that is not normally distributed a nonparametric test. Likert scale data will be transformed into numerical data and evaluated as continuous variables.

Outcome variables	Variable Type	Statistical Test
Primary Outcome Tissue esophageal eosinophils < 15/ hpf	Binary categorical	Two-sided likelihood ratio chi-square test of two independent proportions

Change in EEsAI	Likert scale - continuous	Normally distributed data: t-test Non-normally distributed data: Mann-Whitney U
Change in PedsQL	Likert scale - continuous	Normally distributed data: t-test Non-normally distributed data: Mann-Whitney U
Change in EREFS	Continuous	Normally distributed data: t-test Non-normally distributed data: Mann-Whitney U
Change in eosinophils per hpf	Continuous	Normally distributed data: t-test Non-normally distributed data: Mann-Whitney U
Change in tissue eotaxin level	Continuous	Normally distributed data: t-test Non-normally distributed data: Mann-Whitney U

Although all outcomes will be evaluated and reported using pooled data, a priori planned subgroup analysis will include a stratification of the analysis and results based on adult and pediatric subject groups.

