The participants who choose to consent and enroll in the study will then complete either the EEsAI (age 18 -60) or the PedsQL (age 6-17), both validated questionnaires that assess patient symptoms of EoE. Additionally, all study participants will have their initial Esophagogastroduodenoscopy (EGD) images evaluated via Endoscopic Reference Score (ERFS). This scoring system is a validated tool that has demonstrated moderate to good inter-observer variability. The PI for this protocol will be the physician who assigns a score to pre and post intervention images, in order to limit variations between graders. The 6-8 esophageal biopsies taken at initial EGD will be evaluated by pathology per routine protocol to provide primary diagnosis. Again to limit variation, there are two pathologists serving on this protocol as AIs that will be evaluating the specimens obtained during this research period. Each set of biopsies will then be evaluated by 1 of these 2 pathologists to record the number of eosinophils per high power field (HPF). Immunohistochemical staining on these biopsies for eotaxin-3 will be performed on the Ventana Ultra platform after stain optimization based on previously described protocols. Staining will be evaluated by 1 of 2 pathologists for intensity and percentage of cells staining (Allred scoring system). [name] will be performing research as a credentialed provider at WRNMMC Department of Pathology, although he is assigned to Joint Pathology Center.

The participants will be randomized into 2 groups: 1) omeprazole + swallowed fluticasone and 2) placebo + swallowed fluticasone. The placebo will replicate oral omeprazole. The study participants will be randomly assigned with concealment of allocation to one of the treatment groups, with each group having an equal number of participants (1:1 ratio).

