PI/AI reviews repeat endoscopy findings					X

10.2 Data Collection:

Describe all the data variables, information to be collected, the source of the data, how the data will be operationally measured, and approvals needed for use of information from DoD databases

Method of Collection from Study Participants.

- EEsAI or PedsQL (approval received for research use) standardized symptom questionnaires, based on age of participant, will be used to assess participant symptoms prior to treatment.
- Initial Esophagogastroduodenoscopy (EGD) images will be evaluated via Endoscopic Reference Score (EREFS) by investigators.
- Biopsies taken at initial EGD will be evaluated by pathology for number of eosinophils per high power field (HPF) and tissue eotaxin-3 level.
- Compliance will be checked via phone follow up at 4 weeks, and in person at 8 weeks (completion of therapy) by asking patient to report number of pills remaining and number of actuations remaining on the MDI.
- Participants will be given enough medication to last the full 8 weeks of therapy.
- At the end of 8 weeks of therapy, participants will undergo repeat EGD, with re-evaluation of all markers completed at the start of therapy: EREFS, EEsAI or PedsQL, and tissue for number of eosinophils per HPF and eotaxin-3 staining.

Study variables

- a. Independent
 1. Standard therapy treatment group: Fluticasone topical steroid
 2. Intervention treatment group: Fluticasone topical steroid + PPI
- b. Dependent
 1. EEsAI/PedsQL

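### Adjusting the primary responder test for the baseline eosinophil count, already collected, would be a free gain in power; its size is not known from the documents

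*Combined protocol and SAP*

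**What the plan says.** The outcome table in 11.6 makes the primary outcome binary (count below 15 eos/hpf) and assigns it a two-proportion likelihood ratio chi-square. Sections 11.2 and 11.5 base the sample size on the same test, a "two-sided likelihood ratio chi-square test of two independent proportions", with "alpha of 0.05 and a power of 0.8".

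The planning rates in 11.5 are: for control, "A response rate in the control group of fluticasone alone (reference proportion) was estimated to be 50" percent; for the combination arm, "estimated to be in the range of 70% to 80" percent. The stated result is that the "sample size estimation may vary anywhere from 78 to 180 subjects". Section 11.4 then sets "50 subjects in each arm".

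The baseline count is part of routine data collection. Section 10.2 says: "Biopsies taken at initial EGD will be evaluated by pathology for number of eosinophils per high power field (HPF) and tissue eotaxin-3 level". Section 10.1 has one of two study pathologists record the count for each set of biopsies. In 11.6 that baseline value appears only inside the secondary change in eosinophils per hpf.

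The prompt in 11.1 asks how confounders will be controlled. The answer refers to 11.4, which lists only the arms. If 11.6 was meant, it names no covariate either. Section 2.3 describes block randomization without a stratification factor. The one planned stratified analysis, in 11.6, is by adult and pediatric group.

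**The concern.** Response is judged on the follow-up count against a fixed cut. The baseline count is the earlier value of the same measurement, so it is a natural candidate to predict response: a subject who starts just above the diagnostic threshold has less far to fall than one who starts at several times that level. If baseline does predict response, a raw comparison of proportions leaves the explained variation in the noise.

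This trial could use the efficiency. The enrolment of 100 lies in the lower part of the plan's own 78 to 180 range, so over the lower half of the assumed effect range the trial misses its 80% power target. Chance differences in baseline between arms also go uncorrected, because neither the randomization nor the analysis deals with them.

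**Working it through.** **1. The plan's own sample sizes.** For the likelihood ratio test, with p̄ the mean of the two rates and f(p) = p ln(p/p̄) + (1−p) ln((1−p)/(1−p̄)), the noncentrality per subject per arm is λ = 2[f(p1) + f(p2)]. Then n per arm = (1.960 + 0.842)²/λ = 7.849/λ.

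- 50% vs 80%: λ = 0.2027, n = 38.7, rounded up to 39, total 78. This matches the plan.
- 50% vs 70%: λ = 0.0840, n = 93.4, rounded up to 94, total 188. The plan says 180. An unpooled-variance formula gives 182, and 90 per arm has power 0.785 (likelihood ratio) to 0.799 (unpooled). The figure is close enough to count as reproduced.

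**2. Power of the planned test at 50 per arm.** Power = Φ(√(50λ) − 1.960).

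| Combination-arm response | 50λ | Power, formula | Power, exact |
|---|---|---|---|
| 70% | 4.201 | Φ(0.090) = 0.536 | 0.546 |
| 75% | 6.764 | Φ(0.641) = 0.739 | 0.745 |
| 80% | 10.134 | Φ(1.223) = 0.889 | 0.895 |

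These take 50 evaluable subjects per arm; the documents give no dropout rate.

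**3. Power with baseline in the model.** The strength of association is an assumption, so it is varied. Week-8 response was simulated from a logistic model with standardised log baseline count as covariate, and intercepts set so that the marginal rates stay at the plan's values. The likelihood ratio test for arm was run with and without baseline. With 4,000 trials per cell, the simulation error of one power figure near 55% is √(0.55 × 0.45/4000) = 0.8 points. The ranges below span repeat runs.

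| Odds ratio per SD of log baseline | Control response 1 SD below / above the mean* | Gain at 70% | Gain at 75% | Gain at 80% |
|---|---|---|---|---|
| 1.0 | 50% / 50% | about 0 | about 0 | about 0 |
| 1.65 | 62% / 38% | about 2 | 2 to 3 | about 2 |
| 2.7 | 73% / 27% | 6 to 8 | 6 to 9 | about 5 |
| 4.5 | 82% / 18% | 13 to 16 | about 13 | 7 to 8 |

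*Odds of 1 at the mean, so OR/(1 + OR) and 1/(1 + OR). Gains are in percentage points of power.

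**4. Cross-check with a different model.** Here the week-8 log count is normal with correlation ρ to the baseline log count, and response means falling below a cut. For 70%, 75% and 80% the gains are +2, +3, +2 points at ρ = 0.3; +6 to 7, +7 to 8, +4 at ρ = 0.5; and +15 to 16, +14, +8 at ρ = 0.7. Below ρ = 0.2 the gain is at most about 1 point. The two models agree.

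**5. Limit at 80%.** Planned power there is already about 0.89, so at most about 1 − 0.89 = 0.11 can be gained under any association.

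**6. Type I error.** With both arms at 50%, the adjusted test rejected in 4.8-5.8% of simulated trials and the unadjusted test in 5.2-6.1%. The exact size of the unadjusted test at 50% response is 5.7%.

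**7. Chance imbalance.** The standard error of the between-arm difference in mean standardised baseline is √(2/50) = 0.2 SD. A difference of 0.4 SD, roughly a 1-in-20 event, shifts the raw risk difference by about 5, 8 or 11 points at odds ratios 1.65, 2.7 and 4.5. The hoped-for difference is 20 to 30 points.

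**The case against.** The planned test is valid. Under 1:1 concealed randomization, chance imbalance in baseline is ordinary sampling variation that the test's error rate already covers. The test is also the one on which the sample size was computed. All of this stands. A reader might infer from the imbalance figures that the primary result would be biased, or that the plan contains an error. It does not.

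A reader might also infer that response is defined relative to baseline, so that leaving baseline out contradicts the endpoint. It is not: the endpoint depends on the follow-up count alone.

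The size of the gain rests on an association that the documents do not report. An odds ratio of 4.5 per SD is steep (82% vs 18% response across two SDs in the control arm). Entry requires a count above 15/hpf (10.1), and this cut may weaken the association. This also stands, so no single figure for lost power can be claimed, and a gain near zero is possible.

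Finally, the adjusted test concerns a conditional log odds ratio while the reported effect is a marginal risk difference, so a p-value and CI near the boundary could disagree. That calls for naming in advance which one decides. It is not a reason to forgo the adjustment.

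**Conclusion.** Free improvement, not a correction of an error. The primary test omits the baseline value of the very measurement it analyses, although that value comes from tissue taken before randomization and is available for every subject.

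The gain at 50 evaluable subjects per arm is about 0 to 13-16 points of power if the combination arm responds at 70-75%, and about 0 to 7-8 points at 80%. Both ranges assume odds ratios of 1.0 to 4.5 per SD of log baseline count and the plan's 50% control rate. At 50% vs 75%, an odds ratio of about 2.7 would bring power from 74-75% to about 83%, past the 80% target. At 50% vs 70%, even the strongest association considered leaves it near 69%. Adjustment therefore helps, but it does not replace the missing sample size at the lower end of the range.

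If baseline turns out to be unrelated to response, essentially nothing is lost.

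**What to change.** In 11.6, before unblinding:

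- **Primary test:** the likelihood ratio test for arm in a logistic regression of week-8 response (below 15 eos/hpf) on arm and log baseline eos/hpf. The entry threshold keeps the baseline count above zero, so the log is always defined. Specify that the covariate is the study pathologist's count on the initial biopsies.
- **Effect estimate:** the standardised (marginal) risk difference with a 95% CI by the delta method or bootstrap, so that the estimand stays the difference in proportions. State that the likelihood ratio test decides the primary result.
- **Sensitivity analysis:** the unadjusted likelihood ratio chi-square, noted as the test on which the sample size was based.
- **Subgroups:** say whether the same model is used in the adult and pediatric analyses.

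The cost is a few lines of text and one covariate. It needs no new data, visits or subjects. The timing matters: the same change made after unblinding would look chosen from the results.

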Each treatment group will be treated for 8 weeks. Therapy for the PPI + topical steroid group will be 40mg omeprazole by mouth twice daily and 880mcg swallowed fluticasone twice daily. Therapy for the placebo + topical steroid group will be a sham omeprazole capsule by mouth twice daily and 880mcg nebulized and swallowed fluticasone twice daily (total dosage 1760 mcg). Participants will be instructed to take omeprazole or placebo on an empty stomach each morning, at least 30 minutes prior to eating, but no more than 60 minutes. Participants will also be instructed to rinse mouth with water or brush teeth after taking fluticasone, but not swallow anything within 30 minutes after taking the medication. For study participants age 17 years and younger, the dose for fluticasone will be 440mcg given 2-4 times per day based on 2011 consensus guidelines.(1) The pediatric dose for omeprazole will be 2mg/kg/day divided twice daily, with max dose of 40mg per day.

Compliance will be checked via phone follow up at 4 weeks and in person at 8 weeks (completion of therapy) by asking patient to report number of pills remaining and number of actuations remaining on the MDI. Participants will be given enough medication to last the full 8 weeks of therapy. At the time of repeat endoscopy, patients will be instructed to bring their medications for a full count of remaining pills.

At the end of 8 weeks of therapy, participants will undergo repeat EGD, with re-evaluation of all markers completed at the start of therapy including esophageal eosinophilia, endoscopic assessment (EREFS), validated clinical questionnaire (EEsAI or PedsQL), and immunohistochemistry staining for eotaxin-3. EGDs will be performed to standard of care, with biopsies taken from the esophagus only.

Prior to the EGDs, all pediatric subjects will undergo the routine pre-op evaluations and physicals by Pediatric GI and anesthesia, which is standard of care. All subjects are required to fast beginning the night prior to the EGD which is also standard practice.

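### Section 11.6 tests the five continuous outcomes as unadjusted change scores although their baselines are collected; a baseline-adjusted main analysis would gain power in these supporting outcomes at no cost in patients

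*Combined protocol and SAP*

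**What the plan says.** The table in section 11.6 (Data Analysis Plan) lists five continuous outcomes, each as a change from baseline, and gives each the same entry: "Normally distributed data: t-test Non-normally distributed data: Mann-Whitney U". The text above the table says that normally distributed differences "will be tested using parametric tests and for data that is not normally distributed a nonparametric test". The eosinophil row reads only "Change in eosinophils per hpf", without saying whether the change is absolute or percent.

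Baselines exist for all five measures. Section 10.1 (Study Procedures) has them recorded at entry and provides at week 8 for "re-evaluation of all markers completed at the start of therapy". Allocation is equal: "with each group having an equal number of participants (1:1 ratio)". The symptom scales are split by age, since participants "will then complete either the EEsAI (age 18 -60) or the PedsQL (age 6-17)". Eotaxin-3 staining is scored for "intensity and percentage of cells staining (Allred scoring system)", and section 11.6 types it as continuous.

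No covariate-adjusted model appears in the document. The form's question in 11.1 on confounding is answered by a pointer to 11.4, which lists only the arms. Age group enters only as a subgroup stratification.

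**The concern.** A change score adjusts for baseline with the slope fixed at 1. ANCOVA estimates the slope from the same two measurements on the same patients. If the true slope is below 1, subtracting the whole baseline adds noise and the comparison loses power.

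The hypothesis in section 9.4 covers both histology and symptoms. The symptom half rests on EEsAI in adults and PedsQL in children. If both age groups enrol, each scale is analysed in fewer than the planned 50 per arm, which is where efficiency is scarcest. For eosinophils, counts are skewed and entry requires a raised count. An absolute change can then be dominated by how high the baseline was.

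**Working it through.** **Plan's own figure.** There is none for any continuous outcome. The sample size range in section 11.2 concerns the binary primary outcome and is not used here, except that its response rates (50% on control; treatment "estimated to be in the range of 70% to 80" per cent) anchor the eosinophil scenarios below.

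**Inputs from the documents.** Five change-score tests, 50 per arm, 1:1 allocation. **Assumed, because the documents are silent:** the correlation r between baseline and week 8, the SDs, an effect of 0.5 SD, and 25 per arm as an illustrative size for one symptom scale.

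**Variance.** Let k be the baseline SD divided by the week-8 SD, and set the week-8 SD to 1.
- Variance of change: 1 + k² − 2rk
- Residual variance under ANCOVA: 1 − r²
- Difference: (1 + k² − 2rk) − (1 − r²) = (k − r)², which is never negative. It is zero only when k = r, that is when the slope r/k equals 1.

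So in large samples with 1:1 allocation the change score is never the more efficient. With equal SDs (k = 1) the ratio change/ANCOVA is 2(1 − r)/(1 − r²) = 2/(1 + r). This gives 2/1.3 = 1.54, 2/1.5 = 1.33 and 2/1.7 = 1.18 at r = 0.3, 0.5 and 0.7. On that basis 100 patients under ANCOVA are worth about 154, 133 and 118 under change scores.

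**Power, 0.5 SD effect, two-sided 0.05.** The standardised effect is 0.5/√(2(1 − r)) for change and 0.5/√(1 − r²) for ANCOVA.

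| r | Effect, change | Effect, ANCOVA | 50 per arm, change → ANCOVA | 25 per arm, change → ANCOVA |
|---|---|---|---|---|
| 0.3 | 0.423 | 0.524 | 55 → 74% | 31 → 44% |
| 0.5 | 0.500 | 0.577 | 70 → 82% | 41 → 52% |
| 0.7 | 0.645 | 0.700 | 89 → 93% | 61 → 68% |

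Simulation that includes the cost of estimating the slope lowers the ANCOVA figures by 2 points or less (73, 81 and 93% at 50 per arm; 43, 50 and 67% at 25). Type I error at 25 per arm, r = 0.5, was 5.0% for change and 4.9% for ANCOVA.

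**Eosinophils, by simulation, 50 per arm.** Baseline is log-normal with median 50 and log SD 0.6, truncated at 15. Scenario A has a control week-8 median of 12 and log SD 1.6; the proportion below 15/hpf is about 55% on control, 71% at a log shift of 0.7 and 77% at a shift of 1.0. Scenario B has median 15 and log SD 1.2 (about 49%, 71% and 79%). The planned rule (normality test, then t-test or Mann-Whitney) was applied to absolute and to percent change and compared with ANCOVA on the log scale.

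| Scenario, shift | r | Absolute change | Percent change | Log ANCOVA |
|---|---|---|---|---|
| A, 0.7 | 0 | 20% | 50% | 56% |
| A, 0.7 | 0.4 | 30% | 62% | 63% |
| A, 1.0 | 0 | 33% | 79% | 85% |
| A, 1.0 | 0.4 | 47% | 89% | 91% |
| B, 0.7 | 0 | 27% | 71% | 80% |
| B, 0.7 | 0.4 | 38% | 85% | 87% |
| B, 1.0 | 0 | 41% | 95% | 98% |
| B, 1.0 | 0.4 | 59% | 99% | 99% |

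Up to r = 0.4 the gain over absolute change is 33 points (63 − 30) to 57 points (98 − 41). At higher r it usually narrows. In scenario A, shift 1.0, it is 36 points at r = 0.6 and 14 at r = 0.8. In scenario B, shift 1.0, it is 28 (72 v 100%) and 10 (90 v 100%). It can stay large: 59 v 95% in scenario A, shift 0.7, r = 0.8. A different set of skewed inputs (control median 15, halved by treatment) gave 36 v 68%, 48 v 72% and 60 v 79% at r = 0, 0.3 and 0.5, which are gains of 32, 24 and 19 points. Over percent change the gain is about 0 to 11 points across settings.

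**Where the eosinophil gain comes from.** An unadjusted Mann-Whitney on the week-8 count, compared with log ANCOVA, gave:
- r = 0: 53 v 55% (A, 0.7), 80 v 81% (B, 0.7), 98 v 99% (B, 1.0)
- r = 0.4: 58 v 65%, 82 v 88%, 98 v 99%

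At low r, most of the gain therefore comes from not subtracting the raw baseline. Adjustment itself adds more as r rises.

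**The case against.** The strongest reply is that the planned tests are sound. Randomisation makes the change-score comparison valid, the primary outcome is a separate binary test, and efficiency in secondary outcomes is partly a matter of preference. That stands, and it limits the point to an improvement rather than an error.

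It is also fair that all correlations, SDs and effect sizes are assumed, that the gain vanishes at a slope of 1, and that the symptom-scale gain at 25 per arm is modest: after the finite-sample correction, 43 − 31 = 12, 50 − 41 = 9 and 67 − 61 = 6 points. None of this is a reason to prefer the change score, which in large samples is never the better of the two here.

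A reader might infer that choosing the test from normality checks inflates the false-positive rate. The simulations do not support that: type I error was 4.6 to 5.5% for the rule on absolute change and 4.8 to 5.4% on percent change, against 5.0 to 5.4% for log ANCOVA. A reader might also credit covariate adjustment with the whole eosinophil gain. The week-8 Mann-Whitney comparison shows otherwise at low r.

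Finally, the remedy is not neutral for reporting. A log model estimates a ratio of geometric means rather than a difference in eosinophils per field. That objection is right and is carried into the fix.

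**Conclusion.** The point holds as a free gain in efficiency for supporting outcomes. Taking section 11.6 at its word that the primary outcome is the proportion below 15/hpf, that analysis, its type I error and the 100 patients are untouched.

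For the scale outcomes with equal SDs and a 0.5 SD effect, the gain at 50 per arm is 19, 12 and 4 points at r = 0.3, 0.5 and 0.7 (13, 11 and 7 points at 25 per arm, before the small finite-sample correction). It is nil when the slope on baseline is 1. For eosinophils it is roughly 10 to 57 points if change is absolute, depending on scenario and on r between 0 and 0.8, and about 0 to 11 if change is percent.

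Two stronger readings go too far. The undefined eosinophil change and the normality-based choice of test are gaps in detail that the same edit closes; they are not separate errors. Nor would ANCOVA make the symptom scales well powered: at 25 per arm it still gives only 44 to 68% for r between 0.3 and 0.7.

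**What to change.** In the section 11.6 table, make the main analysis of each continuous outcome a model of the week-8 value with treatment arm and baseline value as terms:
- EEsAI, PedsQL and EREFS: ANCOVA on the scale score.
- Eosinophils: log(count + 1) at week 8 with log baseline. State that the result is a ratio of geometric means, not a difference in eosinophils per field.
- Eotaxin-3 staining score: rank-based ANCOVA.

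Name these models in advance, so that normality checks no longer select the main test. Keep the planned change-score t-test or Mann-Whitney as sensitivity analyses, and state there whether eosinophil change is absolute or percent.

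The cost is an edit to the analysis plan and a different effect measure for eosinophils. The baselines are already collected, and no patients, visits or procedures are added.
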